## 9.7 Evaluation of Best Overall Response

Target Lesions	Non-Target Lesions	New Lesions	Overall Response
CR	CR	No	CR
CR	Non-CR/ Non-PD	No	PR
CR	Not evaluated	No	PR
PR	Non-PD/ or not all evaluated	No	PR
SD	Non-PD or not all evaluated	No	SD
Not all evaluated	Non-PD	No	Non-evaluable
PD	Any	Yes or No	PD
Any	PD*	Yes or No	PD
Any	Any	Yes	PD

\*In exceptional circumstances, unequivocal progression in non-target lesions may be accepted as disease progression.

Subjects with a global deterioration of health status requiring discontinuation of treatment without objective evidence of disease progression at that time should be classified as having “symptomatic deterioration”. Every effort should be made to document the objective progression even after discontinuation of treatment.

In some circumstances it may be difficult to distinguish residual disease from normal tissue. When the evaluation of complete response depends on this determination, it is recommended that the residual lesion be investigated (fine needle aspirate/biopsy) to confirm the complete response status.

### **Confirmatory Measurement/Duration of Response**

To be assigned a status of PR or CR, changes in tumor measurements must be confirmed by repeat assessments that should be performed 4-6 weeks after the criteria for response are first met. In the case of SD, follow-up measurements must have met the SD criteria at least once after study entry at a minimum interval of 6 weeks (see below).

Overall Response First time point	Overall Response Subsequent time point	Best Overall Response
CR	CR	CR
CR	PR	SD/PD/PR*
CR	SD	SD provided minimum criteria for SD duration met, otherwise, PD
CR	PD	SD provided minimum criteria for SD duration met, otherwise, PD
CR	NE	SD provided minimum criteria for SD duration met, otherwise, NE
PR	CR	PR
PR	PR	PR
PR	SD	SD
PR	PD	SD provided minimum criteria for SD duration met, otherwise, PD
PR	NE	SD provided minimum criteria for SD duration met, otherwise, NE
NE	NE	NE

\* If a CR is truly met at first time point, then any disease seen at a subsequent time point, even disease meeting PR criteria relative to baseline, makes the disease PD at that point (since disease must have reappeared after CR). Best response would depend on whether minimum duration for SD was met. However, sometimes 'CR' may be claimed when subsequent scans suggest small lesions were likely still present and in fact the subject had PR, not CR at the first time point. Under these circumstances, the original CR should be changed to PR and the best response is PR.

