- (2) Blood will be taken to assess plasma methionine levels at baseline, cycle 2 day 5, then day 5 of every other cycle, and at end of treatment. Subjects must be fasting. If necessary, these labs may be drawn as early as day 2, but prefer to be as close to day 5 as possible without going over.
- (3) If clinically indicated.
- (4) Optional biopsy prior to study entry.
- (5) Blood for circulating tumor cells will be taken at baseline, day 5 of cycle 2, and at end of treatment. If necessary, these labs may be drawn as early as day 2, but prefer to be as close to day 5 as possible without going over.
- (6) For women of childbearing potential. To be completed within 7 days of randomization. Must be repeated at cycle 1 day 1 if not completed in previous 7 days.
- (7) Subjects whose treatment is interrupted or permanently discontinued due to an adverse event (including lab values) should be followed per section 11.1.1.
- (8) Waist circumference, optional if not possible due to site limitations. Not required at screening.
- (9) CMP to include sodium, potassium, chloride, carbon dioxide, glucose, BUN, creatinine, calcium, albumin, total protein, alkaline phosphatase, aspartate aminotransferase (AST), alanine aminotransferase (ALT), and total bilirubin.
- (10) CT chest with or without contrast and CT with contrast or MRI of Abdomen/Pelvis to be completed during screening and  $\leq$  7 days prior to every third cycle starting at cycle four (approximately every 9 weeks; e.g. cycles 4, 7, 10, etc.). If subjects discontinue study treatment prior to disease progression, scans during follow-up will be completed per standard of care, but RECIST measurements must be completed until disease progression or start of new anti-cancer therapy.
- (11) Homocysteine/cysteine level at: baseline and every 3 cycles while on study (C1, C4, C7, etc.) and at end of treatment.
- (12) One block or 10 unstained slides.
- (13) labs/physical exam/ECOG PS does not need to be repeated if done within 7 days prior to C1D1

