### 9.8.2 Confirmation of Response

To be assigned a status of complete or partial response, changes in tumor measurements must be confirmed by repeat assessments performed no less than four weeks after the criteria for response are first met.

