### 9.8.5 Objective Response Rate

The objective response rate is the proportion of all subjects with confirmed PR or CR according to RECIST 1.1, from the start of treatment until disease progression/recurrence (taking as reference for progressive disease the smallest measurements recorded since the start of treatment).

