### 13.2 Sample size and accrual

The primary objective is to evaluate efficacy of ONC-201 with dietary MR in metastatic TNBC. The study is designed as a single-arm phase II trial. The primary endpoint is ORR. Secondary endpoints include CBR at 4 months, PFS, OS, safety, metabolic indices and CTC TRAIL-receptor expression. The null hypothesis is that the probability of overall response is no more than 0.1, *i.e.*,  $H_0: p \leq 0.1$ , and the alternative hypothesis is  $H_1: p \geq 0.25$ .

In this single arm study, a Simon's two stage design will be utilized. The null hypothesis that the true ORR is 0.1 will be tested against a one-sided alternative. The study will be powered to detect an ORR of 25% with the combination of ONC201 with a methionine-restricted diet, using a power of 80% and a type I error rate of 10%. The first stage sample size will be 13. After testing the combination on 13 subjects in the first stage, the trial will be terminated if 1 or fewer subjects respond. If the trial goes on to the second stage, a total of 34 subjects will be studied (*i.e.* additional 21 subjects will be recruited). If the total number responding or having ORR is less than or equal to 5, the combination of ONC201 with a methionine-restricted diet will be rejected.

The estimated total sample size for the study is 34 subjects.

One subject was enrolled to the ONC201 +MR diet prior to changing the dosing schedule. This subject will be replaced for efficacy analysis, but will be considered part of the safety analysis.

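### ORR counts only confirmed responses, but the 4-6 week confirmation timing in 9.7 does not fit the CT/MRI schedule or 9.8.2, and 13.2 does not say when the stage 1 count closes

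*Combined protocol and SAP*

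**What the plan says.** Section 9.8.5 defines ORR as "the proportion of all subjects with confirmed PR or CR according to RECIST 1.1". Two passages give the timing of confirmation:

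- Section 9.7 (Confirmatory Measurement/Duration of Response): changes "must be confirmed by repeat assessments that should be performed 4-6 weeks after the criteria for response are first met".
- Section 9.8.2: changes "must be confirmed by repeat assessments performed no less than four weeks after the criteria for response are first met". There is no upper limit.

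The table in 9.7 gives PR followed by PR as PR and sets no maximum interval. PR followed by SD is SD. PR followed by a non-evaluable assessment is "SD provided minimum criteria for SD duration met, otherwise, NE".

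Footnote 10 of the study calendar (section 7) sets CT/MRI at screening and then within 7 days "prior to every third cycle starting at cycle four (approximately every 9 weeks; e.g. cycles 4, 7, 10, etc". It lists no confirmation scan. For subjects who stop treatment before progression, "scans during follow-up will be completed per standard of care", with RECIST measurements required until progression or new therapy. The calendar grid reads differently. The on-treatment CT/MRI mark stands in the column for even-numbered cycles from cycle 4, and a further mark stands in the follow-up column, which is headed every 3 months.

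The stage 1 rule in 13.2 is that "the trial will be terminated if 1 or fewer subjects respond", out of 13. The final rule rejects the combination "If the total number responding or having ORR is less than or equal to 5", out of 34. Section 13.2 does not say whether stage 1 responses must be confirmed, when they are counted, or whether accrual pauses. The table of contents lists a 13.8 on interim analysis with a broken link, and section 13 ends at 13.7.3.

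**The concern.** A response enters the primary endpoint only once it is confirmed, so the timing rule for confirmation is part of the endpoint definition. The protocol states that rule twice, differently, and its own imaging schedule can satisfy only one of the two versions. A site or analyst who applies 9.7 literally would not count a PR seen before cycle 4 and again before cycle 7. Under 9.8.2 the same patient is a responder. Sites may also differ in whether they add a repeat scan at 4-6 weeks.

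The stage 1 rule raises a related problem. On scheduled scans, a response first seen at about week 9 is not confirmed until about week 18. If the count of 13 is made in between, that patient is not yet a confirmed responder, and the trial could stop with the deciding confirmation outstanding.

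**Working it through.** **1. Design as written.** Inputs from 13.2: n1 = 13, stop at 1 or fewer; N = 34, reject at 5 or fewer; p0 = 0.10, p1 = 0.25. With X1 ~ Bin(13, p) and X2 ~ Bin(21, p):

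- P(stop at stage 1) = P(X1 ≤ 1) = 0.621 at p = 0.10 and 0.127 at p = 0.25.
- P(declare active) = Σ over x = 2 to 13 of P(X1 = x)·P(X2 ≥ 6 − x) = 0.0957 at 0.10 and 0.8108 at 0.25.

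This reproduces the stated 10% type I error and 80% power. The sample size is not in question.

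**2. Scan spacing under footnote 10.** Inputs: 21-day cycles (5.2), scan up to 7 days before day 1 (footnote 10), day 1 ± 2 days (calendar).

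- C4 day 1 = 1 + 3 × 21 = day 64, so the scan falls on days 57-64 (about week 9).
- C7 day 1 = 1 + 6 × 21 = day 127, so the scan falls on days 120-127 (about week 18).
- C10 day 1 = 1 + 9 × 21 = day 190 (about week 27).
- 9.7 window after a first PR at the C4 scan: 57 + 28 = day 85 to 64 + 42 = day 106. No CT/MRI is scheduled there.
- Nominal gap: 63 days. Shortest: 63 − 7 − 4 = 52, or 63 − 7 − 6 = 50 if three successive cycles each start 2 days early. Longest: 63 + 7 + 4 = 74, more if treatment is delayed.

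Every gap exceeds 42 days, so no scheduled pair fits 9.7. Every gap exceeds 28 days, so every pair meets 9.8.2.

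**3. The grid read as a column.** Scans at C4 and C6 would be 2 × 21 = 42 days apart, exactly the upper limit in 9.7. With windows the gap is 42 ± 11, or 31-53 days, so some pairs would fit and some would not. The mark carries footnote 10, which names cycles 4, 7 and 10, so the footnote probably governs, but the two do not agree.

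**4. How close the bounds are.**

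| True ORR | P(exactly 2 of 13) | P(continue and end with exactly 6 of 34) |
|---|---|---|
| 25% | 0.206 | 0.080 |
| 10% | 0.245 | 0.054 |

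These follow from the design alone and would be the same under perfect confirmation wording.

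**5. Stage 1 counted too early (illustration only).** Suppose that only a share s of the eventual confirmed responses is known at the stage 1 count, and that all are known at the end. The documents give no value for s. At a true ORR of 25%:

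| s (assumed) | P(stop at stage 1) | Power |
|---|---|---|
| 1 | 0.127 | 0.81 |
| 0.9 | 0.174 | 0.77 |
| 0.75 | 0.269 | 0.69 |
| 0.5 | 0.504 | 0.47 |

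**6. Time to a complete stage 1 count.** A first response at C4 is confirmed at about week 18, and one at C7 at about week 27. Even accrual is 34/30 = 1.13 subjects per month (30 months, synopsis). At 4.345 weeks per month, 18 weeks brings 1.13 × 18/4.345 = 4.7 further subjects and 27 weeks brings 7.0.

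**The case against.** The strongest reply is that nothing binding conflicts. In 9.7 confirmation is a 'must' but the 4-6 weeks is a 'should', 9.8.2 supplies the binding minimum, and the table in 9.7 accepts PR then PR without an upper limit. A PR at week 9 repeated at week 18 meets all of this. That stands, and it is why this is a wording correction and not a demonstrated loss.

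A second reply is that a confirmation scan depends on when response occurs, so 9.7 could itself be the instruction to perform one. Nothing in footnote 10 forbids it. This is fair, but the calendar does not provide the scan, and nothing says what happens to a response confirmed only at the next scheduled visit.

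Third, lesions measured by calipers can be re-measured at the physical exam each cycle. That is correct, and the point is limited to disease measured by CT or MRI.

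Fourth, 9.8.5 already says 'confirmed', so repeating it in 13.7.1 is only a clarification. Agreed.

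A reader might go further and infer that no response can be confirmed, or that power falls well below 80%. The documents do not support this. It would require reading 'should' as a requirement and assuming that no site ever adds a scan, and the documents give no rate at which confirmations would be lost. A reader might also take the 0.206 and 0.080 as misclassification risks. They are only chances of landing on a bound.

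**Conclusion.** The point holds as an inconsistency in the timing rule of the primary endpoint, together with an undefined stage 1 count. Under footnote 10, scheduled CT/MRI scans are about 50-74 days apart (longer with treatment delay): all miss the 9.7 window and all meet 9.8.2. The calendar grid adds two disagreements, even-numbered cycles against cycles 4, 7 and 10, and a 3-monthly follow-up mark against standard of care. These passages must be reconciled.

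No loss of power or inflation of type I error is shown. With confirmation read as in 9.8.2, and a stage 1 count that waits for pending confirmations, the design keeps its 0.096 and 0.811, provided that 10% and 25% are meant as confirmed response rates. The matter deserves correction before the stage 1 decision because one responder can decide either bound.

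**What to change.** 1. In 9.7, replace the 4-6 week wording with the 9.8.2 rule: at least four weeks after first CR or PR, no upper limit, and the next scheduled scan qualifies.
2. Align the CT/MRI column of the calendar with footnote 10, and reconcile the 3-monthly follow-up mark with the standard-of-care wording in footnote 10 and 6.3.
3. In 13.2, state that stage 1 counts confirmed CR or PR. Stopping for 1 or fewer of 13 is not declared while any of the 13 (a) has an unconfirmed CR or PR with its next scheduled or follow-up assessment pending, or (b) is on study without progression and could still respond up to a scan named in advance. Say whether accrual pauses.
4. Optionally, repeat 'confirmed' in 13.7.1.

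The cost is wording and time. No scans are added, and the sample size and bounds do not change. The stage 1 decision would come about 18 weeks after the 13th subject starts, or about 27 weeks if first responses at C7 are allowed. About 5 to 7 more subjects would enrol meanwhile at even accrual unless accrual pauses. One weakness remains: responses lasting 4-9 weeks still depend on whether a site repeats the scan early. Adding a confirmation scan to the calendar after a first response would address that, at the price of an extra scan for each responder.

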## 9.8 Definitions for Response Evaluation – RECIST 1.1

### 9.8.1 First Documentation of Response

The time between initiation of therapy and first documentation of PR or CR.

### 9.8.2 Confirmation of Response

To be assigned a status of complete or partial response, changes in tumor measurements must be confirmed by repeat assessments performed no less than four weeks after the criteria for response are first met.

### 9.8.3 Duration of Response

Duration of overall response—the period measured from the time that measurement criteria are met for complete or partial response (whichever status is recorded first) until the date that recurrent or progressive disease is objectively documented (taking as reference for progressive disease the smallest measurements recorded since treatment started).

### 9.8.4 Duration of Overall Complete Response

The period measured from the time that measurement criteria are met for complete response until the first date that recurrent disease is objectively documented.

### 9.8.5 Objective Response Rate

The objective response rate is the proportion of all subjects with confirmed PR or CR according to RECIST 1.1, from the start of treatment until disease progression/recurrence (taking as reference for progressive disease the smallest measurements recorded since the start of treatment).

### 9.8.6 Progression-Free Survival

A measurement from the date of treatment initiation until the criteria for disease progression is met as defined by RECIST 1.1 or death occurs. Subjects who have not progressed will be right-censored at the date of the last disease evaluation.

### 9.8.7 Overall Survival

Overall survival is defined by the date of treatment initiation to date of death from any cause.

## 10. DRUG INFORMATION

### 10.1 ONC201

#### 10.1.1 Drug Product Supply and Inventory

Handling: Qualified personnel, familiar with procedures that minimize undue exposure to themselves and the environment, should undertake the preparation, handling, and safe disposal of the chemotherapeutic agent in a self-contained and protective environment.

Availability: ONC201 is provided by Oncoceutics Inc.

Accountability: The investigator, or a responsible party designated by the investigator, should maintain a careful record of the inventory and disposition of the agent using the NCI Drug Accountability Record Form (DARF) or another comparable drug accountability form. (See the NCI Investigator's Handbook for Procedures for Drug Accountability and Storage).

Destruction and Return: Unused supplies of the agent should be returned to the Sponsor within 60 days of the completion of the study. Unused supplies of the agent may also be destroyed on-site upon completion of the study, after accountability has been audited by the Sponsor or designated representative.

Dispensing:

ONC201 must be dispensed only from official study sites and to eligible subjects under the supervision of the site investigator. ONC201 should be stored in a secure area according to local regulations. It is the responsibility of the site investigator to ensure that study drug is only dispensed to subjects.

#### 10.1.2 Pharmaceutical information

The study drug ONC201 is provided as 125 mg free base (approximately 150 mg of dihydrochloride), with or without microcrystalline cellulose, filled into hydroxypropyl methylcellulose (HPMC) capsule shells. Alternative strengths may be manufactured.

[figure not shown]
The ONC201 drug product capsules are intended for oral administration. The product is stored in a multi-dose container. The capsules are packaged in high-density polyethylene (HDPE) white opaque bottles, closed with an induction seal and capped with a white ribbed SecuRx® polypropylene (PPE) cap.

The capsules are to be stored in the original closed container at room temperature (15 to 30°C).

The study drug bottle label bears the following information. If alternative strengths are manufactured, the dosage on the label will be inserted in place of '125 mg'.

ONC201 Capsules, 125 mg
For Oral Use Only
Caution: New Drug—Limited by Federal (or United States) law to investigational use.
Storage: Preserve in original tightly closed containers at room temperature (15 to 30°C)
Sponsor: Oncoceutics, Inc.
Batch # xxx-xxx-xxxx-xx Mfg date: XX-XXXX

## Drug Substance Description

Compound Code(s)	ONC201•2HCl
Alternative Name(s)	ONC201 TIC10 NSC-350625
Chemical Name(s)	7-benzyl-4-(2-methylbenzyl)-1,2,6,7,8,9-hexahydroimidazo[1,2-a]pyrido[3,4-e]pyrimidin-5(4H)-one 2HCl
Molecular Formula	C 24 H 26 N 4 O (free base) C 24 H 26 N 4 O•2HCl (salt)
Molecular Weight	386.49 (free base) 459.41 (salt)
Molecular Structure	

**Form:** ONC201 will be provided as hydroxypropyl methylcellulose (HPMC) capsules filled with the active ingredient (ONC201 dihydrochloride), intended for oral administration. The ONC201•2HCl drug substance is a white to off-white solid. The drug product will be packaged as 25 capsules per bottle. The capsules are filled into 30cc high-density polyethylene (HDPE) white opaque bottles with induction seal and 28mm white ribbed SecuRx polypropylene (PPE) cap.

**Storage and Stability:** Based on the current stability data at 40°C/75%RH room temperature (25°C/60%RH) will be used for the drug product storage. Drug product stability studies found no change after 1 month at 40°C/75%RH when stored with or without desiccant. Similarly no changes have been observed when stored a room temperature for 1 year. Clinical trial batches will be produced without desiccant. No shelf-life has been established for this product at this point. However, representative

clinical trial batches have been placed on stability. Any batches that are out of specifications will be removed from the trial.

For the ONC201 drug substance, stability results show little to no change in assay, impurities or appearance. The only changes observed under the accelerated conditions (40°C/75%RH) where a slight increase in moisture content was observed, from 1.2% at time 0, to 6.5% at 2 months, and to 6.2% at 3 months. The moisture content plateaued at approximately the monohydrate. The increase in moisture content did not result in increased impurity levels or decreased potency. These results suggest robust stability of the drug substance when stored at room temperature and accelerated conditions.

## **10.2 Hominex-2 shakes**

Subjects will receive an individualized dietary prescription that incorporates a methionine-free amino acid-modified medical food (Hominex-2, Abbott Nutrition) supplemented with low-methionine foods. Hominex-2 is an amino acid modified medical food that contains a mixture of L-amino acids but lacks methionine. It is used to provide nutritional support for individuals with vitamin B6-nonresponsive homocystinuria or hypermethioninemia. Additional information is available at: <http://abbottnutrition.com/brands/products/hominex-2>

# **11. ADVERSE EVENTS**

## **11.1 Definitions**

### **11.1.1 Adverse Event (AE)**

An AE is any untoward medical occurrence whether or not considered related to the study drug that appears to change in intensity during the course of the study. AEs will be graded using the NCI CTCAE v5. The following are examples of AEs:

- Unintended or unfavorable sign or symptom
- A disease temporally associated with participation in the protocol
- An intercurrent illness or injury that impairs the well-being of the subject

Hospitalization for elective surgery or routine clinical procedures that are not the result of an AE (e.g., surgical insertion of central line) should not be recorded as an AE.

All subjects who discontinue study treatment, including those who refuse to return for a final visit, should be contacted for safety evaluations (i.e., assessment of AEs and/or SAEs, concomitant medications) within 30 days after the last dose of study drugs. Subjects whose treatment is interrupted or permanently discontinued due to an adverse event should be followed at least weekly for four weeks via telephone or in-person visit per physician discretion. Subsequently they should be followed at a minimum of 4-week intervals until resolution or stabilization of the event. If subject discontinues study treatment due to an abnormal lab value, appropriate laboratory

testing should be repeated per physician discretion (minimum ≤ once per week) until resolution to ≤ grade 1 or the treating physician determines the value is not expected to improve.

